Number of Patients Having DLT	n=2	n=3	n=4	n=5	n=6	n=7	n=8	n=9	n=10	n=11	n=12
0	Е	Е	Е	Е	Е	Е	Е	Е	Е	Е	Е
1	n/a	S	S	S	Е	Е	Е	Е	Е	Е	Е
2	U	D	D	S	S	S	S	S	S	S	S
3		U	U	D	D	S	S	S	S	S	S
4			U	U	U	D	D	D	D	D	S
5				U	U	U	U	U	D	D	D
6					U	U	U	U	U	U	D
7						U	U	U	U	U	U

D: De-escalate the dose; E: Escalate the dose; S: Stay at the dose;

U: Unacceptable toxicity; n/a: Not applicable

Patients experiencing a DLT may be managed with dose modification (after dose interruption) or discontinuation. Subsequent dose levels may not be opened until the first 2-4 patients entered at the current dose level have been treated and observed for at least two complete cycles and the number of DLTs among those patients in their first two cycles has been determined.

If a patient withdraws from the study before Day 28 for reasons other than investigational product-related toxicity (see Section 3.2 DLT Definition), another patient may be enrolled to replace that patient at the current dose level. In principle, all patients must be evaluated for 28 days. However, if a patient withdraws close to Day 28 for reasons other than toxicity and is due to a clear unrelated drug event (eg, traffic accident, clear disease progression), the patient may be deemed evaluable for safety if safety assessments have been unremarkable.

and the investigator and sponsor's medical monitor both agree that the patient is evaluable for DLT safety observation.

The dose escalation portion of the study is completed when at least 9 evaluable patients have been treated at the highest dose associated with a mean DLT rate of 25%.

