#### 3.2. DLT Definition

Severity of adverse events will be graded according to CTCAE version 4.03 (see Appendix 2). For the purpose of dose escalation, any of the following adverse events occurring in the first two cycle of treatment (28 days) will be classified as DLTs, unless there is a clear alternative explanation (eg, related to underlying disease/progression):

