### 9. DATA ANALYSIS/STATISTICAL METHODS

## 9.1. Analysis Sets

a. Safety analysis set.

The safety analysis set includes all enrolled patients who receive at least one dose of study medication.

b. Full analysis set.

The full analysis set includes all enrolled patients.

c. Per protocol analysis set (evaluable for MTD).

The per protocol analysis set includes all enrolled patients who receive at least one dose of study medication and who do not have major treatment deviations during first cycle. Patients with major treatment deviations in DLT observation period are not evaluable for the MTD assessment and will be replaced as needed to permit MTD estimation. Major treatment deviations include:

- Administration of less than 75% of the planned dose of PF-04518600 provided that the reduction is not due to toxicity attributable to PF-04518600.
- Administration of more than 150% of the planned dose of PF-04518600.
- d. PK analysis sets.

The PK parameter analysis population is defined as all enrolled patients treated who have sufficient information to estimate at least 1 of the PK parameters of interest.

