# 9.2.2. Statistical Method for Estimating the MTD

### 9.2.2.1. Part A Monotherapy

As previously described, the estimated MTD is the highest tested dose level with mean DLT rate ≤0.25 in at least 9 DLT evaluable patients. It is also assumed that at the estimated MTD, less than 17% patients will experience Grade 4 cytokine release syndrome, infusion reaction or allergic reaction during the 28 day DLT observation period, and the first 98 days after initial treatment. It is also assumed that at the estimated MTD less than 33% of patients will experience grade 3 cytokine release syndrome, infusion reaction, or allergic reaction during the first 98 days after treatment. We assume that higher doses of either PF-04518600 result in higher toxicity rates. But, due to the relatively low number of patients that may be potentially allocated to any dose combination, this assumption may be violated.

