# 9.2.2.2. Part B Combination Therapy

The estimated MTD is the highest tested dose combination level with mean DLT rate ≤0.25 in at least 9 DLT evaluable patients. It is also assumed that at the estimated MTD the toxicity of PF-04518600/utomilumab combination follows the monotonicity assumption that a higher dose level of either PF-04518600 or utomilumab will result in a higher toxicity rates.

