5. ANALYSIS SETS

5.1. Full Analysis Set

The Full Analysis Set (FAS) is defined as all enrolled patients who receive at least one full or partial IV infusion of study drug PF-04518600.

5.2. 'PER PROTOCOL' Analysis Set evaluable for MTD

The per protocol analysis set includes all enrolled patients who receive at least two cycles of study medication and who do not have major treatment deviations during first two cycles.

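### SAP 5.2's MTD-evaluable set drops a patient whose DLT ends treatment before two cycles, and SAP 7.2.1 does not say whether that set or the full analysis set supplies the DLT rate

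*SAP*

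**What the plan says.** **Window.** Protocol 3.2 sets the window for escalation: "any of the following adverse events occurring in the first two cycle of treatment (28 days) will be classified as DLTs". Protocol 3.2.1 adds late immune-related DLTs from Day 29 to Day 98, and the A1 and B1 primary endpoint is DLTs over 98 days.

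**MTD rule.** Protocol 9.2.2.1 (Part A): "the estimated MTD is the highest tested dose level with mean DLT rate ≤0.25 in at least 9 DLT evaluable patients". Protocol 9.2.2.2 (Part B): "The estimated MTD is the highest tested dose combination level with mean DLT rate ≤0.25 in at least 9 DLT evaluable patients".

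**Who is evaluable, protocol.** Section 9.1c requires one dose and no major treatment deviation. Receiving under 75% of the planned dose is such a deviation only "provided that the reduction is not due to toxicity attributable to PF-04518600". Section 3.1.5.1 allows replacement in this case: "If a patient withdraws from the study before Day 28 for reasons other than investigational product-related toxicity". Section 9.1c limits its deviation test to the first cycle, but its next sentence reads: "Patients with major treatment deviations in DLT observation period are not evaluable for the MTD assessment".

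**Who is evaluable, SAP.** Section 5.2, the only SAP set labelled as evaluable for the MTD, is "all enrolled patients who receive at least two cycles of study medication and who do not have major treatment deviations during first two cycles".

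**Which set is used.** SAP 7.2.1 puts the primary analysis on the full analysis set and describes it as a summary of adverse event incidence. Its sentence on DLTs and the MTD names no set. SAP Table 1 counts patients treated at a dose level. SAP section 2 says the SAP supersedes the protocol's statistical considerations and that substantial differences will be identified.

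**Safety set.** Protocol 9.1a: "The safety analysis set includes all enrolled patients who receive at least one dose of study medication". SAP 5.1 and 5.3 require a full or partial infusion of PF-04518600.

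**The concern.** A DLT is the event being counted, and it is also a reason for a patient to miss the second dose. Making two cycles a condition of entry therefore removes patients because they had the outcome. They leave numerator and denominator together, so the dose can only look safer.

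Early stopping is foreseeable. Table 6 in protocol 5.4.5.6.2 calls for permanent discontinuation after many Grade 3 and 4 events in Part B, with exceptions, and Appendix 4 ends treatment in either part after a Grade 3 or 4 allergic or cytokine release reaction. Protocol 3.3 has a separate MTD override, which limits the harm, but it covers only Grade 3 and 4 cytokine release, infusion and allergic reactions.

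At stake is the reported DLT rate and MTD, which belong to the primary objective of A1 and B1.

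**Working it through.** The plan states no figure for this point, so there is none to reproduce. The check compares the wording and then sizes the effect.

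**1. One patient under each rule.** Take a patient treated on Day 1 who has a Cycle 1 DLT and never receives the second dose.

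| Rule | Counted? |
|---|---|
| Protocol 9.1c (one dose; toxicity-related under-dosing exempt) | Yes |
| Protocol 3.1.5.1 (replacement only when the reason is not product toxicity) | Yes, not replaced |
| SAP Table 1 (treated patients) | Yes |
| SAP 5.1 full analysis set | Yes, if any PF-04518600 was infused |
| SAP 5.2 | No |

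SAP 5.6 and 5.6.2 promise a deviation list and a review before lock. That does not restore the patient, because the two-cycle minimum is an exposure condition and not a deviation. The SAP also leaves open whether receiving two cycles means that the second dose was given or that 28 days were completed.

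**2. Apparent rate if set 5.2 is used.** Let p be the true DLT probability and f the share of DLT patients who stop too early to enter the set. The documents do not give f; 25% and 50% are assumed.

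Apparent rate = p(1 − f) / (1 − pf). With p = 0.40:
- f = 25%: 0.30 / 0.90 = 33.3%
- f = 50%: 0.20 / 0.80 = 25.0%

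**3. Effect on the MTD rule (at most 0.25, at least 9 evaluable).** The documents do not define mean DLT rate. It could be the raw proportion x/n, or the posterior mean under the beta(0.75, 0.65) prior of protocol 9.2.1.1, which is (x + 0.75)/(n + 1.4). Drop one early-stopping DLT patient:

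| Counts | Raw proportion | Posterior mean |
|---|---|---|
| 3/10 → 2/9 | 30.0% → 22.2%: flips to pass | 32.9% → 26.4%: still fails |
| 3/11 → 2/10 | 27.3% → 20.0%: flips to pass | 30.2% → 24.1%: flips to pass |

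**4. Chance that a level with a true 40% rate meets the rule.** Assume 10 treated, the size to which B1 levels may be expanded, and no replacement. At most one patient can be dropped if 9 are to remain. Let E be the number dropped, Binomial(10, pf). The DLTs among those left are Binomial(10 − E, q), with q the apparent rate from step 2.

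Chance = P(E = 0) × P(Bin(10, q) ≤ 2) + P(E = 1) × P(Bin(9, q) ≤ c), where c = 2 on raw proportions and c = 1 on posterior means.

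| | Protocol counting (f = 0) | f = 25% | f = 50% |
|---|---|---|---|
| Raw proportion | 16.7% | 25.0% | 21.8% |
| Posterior mean | 16.7% | 16.0% | 13.7% |

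For example, at f = 25% on raw proportions: 0.349 × 0.299 + 0.387 × 0.377 = 0.250. On posterior means there is no inflation, because dropping a patient to reach 9 evaluable lowers the allowed count to 1 and the nine-patient minimum blocks the rest.

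**5. Safety set, Part B.** The B1 Schedule of Activities has utomilumab infused first. A patient stopped by a reaction to it on Day 1 received study medication under protocol 9.1a but no PF-04518600, and so is outside SAP 5.1 and 5.3.

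**The case against.** The strongest reply is that nothing in SAP section 7 invokes set 5.2. SAP 7.2.1 names the full analysis set, SAP 5.9 makes DLT the primary endpoint of A1 and B1, and the DLT sentence sits in that same paragraph. A reader might infer that the SAP names no set at all for its primary analysis; that is not supported. What stands is narrower. The DLT sentence assigns no set, the MTD rule speaks of evaluable patients, and the full analysis set is not an evaluability set, since it keeps early non-DLT withdrawals whom 3.1.5.1 allows to be replaced. Set 5.2 carries the MTD label and is never reconciled with either.

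Other stronger readings also fail:
- **Escalation is distorted.** Table 1 counts treated patients, so it is not.
- **The chance of passing rises far more than step 4 shows.** That would need dropped DLT patients to be replaced, and 3.1.5.1 does not provide replacement for toxicity withdrawals.
- **One dropped patient always flips 3/10.** Only on raw proportions.
- **The cytokine release table has no analysis set.** Protocol 9.6 puts safety summaries on the safety analysis set.

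The step 4 probabilities are also not operating characteristics. They fix 10 patients at a level that Table 1 would often have left earlier, for example at 2/4 or 3/6.

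**Conclusion.** The point holds as a wording conflict with a one-way bias. SAP 5.2 excludes patients whom protocol 9.1c and 3.1.5.1 count, without the flag that SAP section 2 promises. If it supplies the reported DLT rate, a true 40% appears as 33% or 25% under the assumed f. Whether an MTD call changes depends on the counts and on the undefined mean DLT rate: 3/11 to 2/10 flips on either reading, 3/10 to 2/9 on one only.

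A reader might infer that the trial's MTD is wrong. The documents do not support that. Protocol 1.2.1.3 reports no A1 DLTs at the 24 May 2017 cut-off, the B2 dose is already chosen, and the supplied text has no B1 DLT data. The actual impact is unknown. The safety-set gap in Part B is real but secondary.

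**What to change.** 1. **SAP 5.2.** Define the set as treated patients who either (a) had a DLT, including a late immune-related DLT counted toward the MTD under protocol 3.2.1 and the 98-day endpoint, regardless of dosing completed; or (b) completed the 28-day window, or were deemed evaluable under protocol 3.1.5.1, without a major treatment deviation. Carry over the toxicity exemption of protocol 9.1c.
2. **SAP 7.2.1.** Name this set for the DLT rate and the MTD, and state whether mean DLT rate is the observed proportion or the posterior mean.
3. **Protocol 9.1c.** Reconcile the first-cycle wording with the DLT observation period.
4. **SAP 5.1 and 5.3, Part B.** Require at least one full or partial infusion of PF-04518600 or utomilumab.

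The cost is a few lines of SAP text before database lock and one harmonised protocol sentence. No new data are needed, and the replacement rule stays as it is.

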5.3. Safety Analysis Set

The Safety Analysis Set is the same as the Full Analysis Set.

5.4. OTHER ANALYSIS SETS

5.4.1. PK Concentration Analysis Set

The PK Concentration Analysis Set is defined as all patients randomized and treated who have at least 1 measurable concentration.

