#### 5. STUDY TREATMENTS

For the purposes of this study, and per International Conference on Harmonization (ICH) guidelines investigational product is defined as a pharmaceutical form of an active ingredient or placebo being tested or used as a reference in a clinical trial, including a product with a marketing authorization when used or assembled (formulated or packaged) in a way different from the approved form, or when used for an unapproved indication, or when used to gain further information about an approved use (ICH E6 1.33). Eligible patients will be enrolled to receive PF-04518600 (and utomilumab for Part B patients) in an open-labeled, unblinded manner. Patients will be registered and successively assigned to the next available treatment slot at a dose level or dose combination level decided on after the previous cohort's safety evaluation and ongoing observations of earlier enrolled patients. For monotherapy, patients will be dosed at 0.01 mg/kg PF-04518600 in the first cohort. For combination therapy, patients will be dosed at 0.1 mg/kg PF-04518600 and 20 mg utomilumab in the first dose combination level. Selected dose for PF-04518600 in the B2 combination therapy dose expansion cohorts is 30 mg (a flat dose equivalent to 0.3 mg/kg) intravenously (IV) Q2W in combination with PF-05082566 20 mg IV every 28 days.

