# 9.5. Analysis of Pharmacokinetics

# 9.5.1. PF-04518600 and Utomilumab PK Analysis

Serum pharmacokinetic parameters including the maximum concentration ( $C_{max}$ ), and area under the concentration versus time curve within a dose interval ( $AUC_{\tau}$ ) for PF-04518600 (Parts A and B) and utomilumab (Part B only) will be estimated using non-compartmental analysis. If data permit or if considered appropriate, minimum concentration ( $C_{min}$ ), average concentration ( $C_{av}$ ), AUC from time zero extrapolated to infinity ( $AUC_{inf}$ ), terminal elimination half-life ( $t_{1/2}$ ), clearance (CL), apparent volume of distribution ( $V_{ss}$ ), and accumulation ratio ( $R_{ac}$ ) will be also estimated. The PK parameters will be summarized descriptively by dose, and cycle.

The concentrations of PF-04518600 (Parts A and B) and utomilumab (Part B only) will be summarized descriptively by dose, cycle, and nominal time. Individual patient and median profiles of the concentration-time data will be plotted by dose and cycle using nominal times. Median profiles will be presented on both linear-linear and log-linear scales.

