2. INTRODUCTION

This document describes the planned statistical analyses for Protocol B0601002 Amendment 5, dated 16 August 2017. This statistical analysis plan (SAP) amendment is meant to supplement the study protocol. This SAP supersedes the statistical considerations identified in the protocol and, where considerations are substantially different they will be identified as such. Any deviations from this analysis plan will be described in the clinical study report (CSR). Any post-hoc, or unplanned analyses performed that are not specified in this SAP will be clearly identified in the CSR. This plan is developed and finalized prior to database lock of the clinical database. This SAP is written with consideration of the recommendations outlined in the International Conference on Harmonisation (ICH) E9 Guideline (Guidance for Industry: Statistical Principles for Clinical Trials) and on the ICH E3 Guideline (Guidance for Industry: Structure and Content of Clinical Study Reports).

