Part A1 monotherapy dose escalation phase will enroll approximately 58 adult patients with locally advanced or metastatic cancers hepatocellular carcinoma (HCC), melanoma, clear cell renal cell carcinoma (RCC) or head and neck squamous cell carcinoma (HNSCC). The actual number of patients enrolled will depend on the observed safety and tolerability profile of PF-04518600, the number of dose levels that will be tested and expanded to characterize the pharmacodynamic or immunomodulatory (IM) effects, and the number of dose levels required to identify the maximum tolerated dose (MTD) or optimal biological dose (OBD). Six dose levels are proposed: 0.01, 0.1, 0.3, 1.5, 3.0 and 10.0 mg/kg. Each cohort will include an initial cohort of 2-4 patients that may be expanded to approximately 10 patients. Approximately 3 patients enrolled in Japan will be included for at least 2 dose levels. A modified toxicity probability interval (mTPI) method,¹ targeting a dose limiting toxicities (DLT) rate of 25% and an acceptable DLT interval (20% 30%), will be utilized for dose escalation.

Part A2 Monotherapy Dose Expansion

Part A2 monotherapy dose expansion phase will randomize HCC patients 1:1 to flat dose levels of either 30 mg (Arm 1) or 250 mg (Arm 2) of PF 04518600 given every 2 weeks. Both doses were chosen based on data from Part A1. Each arm in Part A2 will include approximately 20 HCC patients.

Part B Combination Therapy

Part B1 Combination Therapy Dose Escalation

Part B1, the combination therapy dose escalation phase, will enroll approximately 53 patients. At least 6 patients must have been evaluated for the 28 day DLT observation period at the 0.3 mg/kg dose level in Part A1 PF-04518600 (OX40 agonist) monotherapy before Part B1 can be initiated. Part B1 will study sequential dose levels of PF-04518600 (0.1, 0.3, 1.0 and 3 mg/kg) combined with either 20 mg or 100 mg of

utomilumab (4-1BB agonist) in adult patients with non-small cell lung cancer (NSCLC), HNSCC, melanoma, bladder, gastric or cervical cancer who are unresponsive to currently available therapies or for whom no standard therapy is available. The starting dose level will be 0.1 mg/kg of PF-04518600 and 20 mg of utomilumab, given no sooner than 30 minutes apart.

A mTPI method, targeting a DLT rate of 25% and an acceptable DLT interval (20%-30%) will be utilized for dose escalation.

Part B2 Dose Expansion

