Part B2 combination therapy dose expansion phase will further evaluate safety and anti-tumor activity of the combination of 30 mg PF-04518600 and 20 mg of utomilumab. Part B2 will be divided into 2 arms:

Arm 1 will enroll melanoma patients who have either:

- a. *Ocular melanoma; and have received no more than one line of systemic therapy for metastatic disease. Patients must not have received immune modifying agents (eg, anti-PD-L1, anti-PD1, anti-CTLA4, TNF agonist, etc.) for metastatic disease; or*
- b. *Cutaneous/acral melanoma; and have 1) only previously received systemic therapy for advanced/metastatic disease with the following therapies: BRAF and MEK inhibitors, anti-PD-L1, anti-PD-1, or anti-CTLA4 and 2) have received checkpoint inhibitor (anti-PD-L1, anti-PD-1, or anti-CTLA4) based treatment as most recent line of therapy on which disease progressed, as long as progression did not occur in the first 3 months of receiving checkpoint inhibitor treatment.*

Arm 2 will enroll NSCLC patients who have:

- a. *Previously received prior anti-PD-L1 or anti-PD-1 mAb as most recent therapy; and,*
- b. *did not have progressive disease as best overall response on recent PD-L1/PD-1 therapy (ie, stable disease ≥ 3 months, PR, or CR), and 3) who subsequently progressed on PD-L1/PD-1 therapy.*

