5.4.2. PK Parameter Analysis Set

The PK parameter analysis population is defined as all enrolled patients treated who have sufficient information to estimate at least 1 of the PK parameters of interest.

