7.2.5.2. Pharmacokinetic Concentrations

To assess the single dose PK profile of PF-04518600 PK concentrations will be listed, summarized and plotted for subjects in the PK analysis set (as defined in [Section 5.4](#)), where missing and BLQ values will be handled as detailed in [Section 7.1](#) above.

Presentations for PF-04518600 will include:

- A listing of all concentrations sorted by dose, subject ID, cycle, and nominal time post-dose. The listing of concentrations will include the actual sample collection times, and the time of dosing. Deviations from the nominal time will be given in a separate listing.
- A summary of concentrations by dose, cycle, and nominal time post-dose, where the set of statistics will include n, mean, median, standard deviation, coefficient of variation (cv), minimum, maximum and the number of concentrations above the lower limit of quantification.

- Median concentrations against nominal time post-dose by dose (based on the summary of concentrations by dose, cycle, and time post-dose), with all doses presented on the same plot. Two plots will be generated, so that the concentrations can be presented on linear and logarithmic scales.
- Mean concentrations against nominal time post-dose by dose (based on the summary of concentrations by dose, cycle, and time post-dose), with all doses presented on the same plot. Two plots will be generated, so that the concentrations can be presented on linear and logarithmic scales.
- Plots of individual concentrations against actual time post-dose (separate plots for each dose). Two plots per dose will be generated, so that the concentrations can be presented on linear and logarithmic scales.
- Plots of concentration against actual time post-dose by subject (separate line for each dose). Two plots per subject will be generated, so that the concentrations can be presented on linear and logarithmic scales.

For summary statistics and median plots by sampling time, the nominal PK sampling time will be used. For individual subject plots by time, the actual PK sampling time will be used.

CCI

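### The SAP's PK concentration set requires randomisation, which only Part A2 has, and its concentration outputs name PF-04518600 only, leaving out utomilumab in Part B

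*SAP*

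**What the plan says.** **Analysis sets.** SAP 5.4.1: "The PK Concentration Analysis Set is defined as all patients randomized and treated who have at least 1 measurable concentration". The next set, the PK Parameter Analysis Set in SAP 5.4.2, is "all enrolled patients treated who have sufficient information to estimate at least 1 of the PK parameters of interest". The PD/biomarker set in SAP 5.4.3 also starts from enrolled patients. Protocol 9.1 has a single PK set, for parameters, with no randomisation condition.

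**Allocation.** SAP 2.1 says that Part A2 "will randomize HCC patients 1:1 to flat dose levels of either 30 mg (Arm 1) or 250 mg (Arm 2"). For the study generally, protocol Section 5 says: "Patients will be registered and successively assigned to the next available treatment slot at a dose level or dose combination level". Protocol 5.1 adds that the sponsor allocates the dose level. The Part B2 arms are defined by tumour type; SAP 2.1 begins the first with "Arm 1 will enroll melanoma patients who have either", and the second is NSCLC. Both receive the same regimen.

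**Outputs.** SAP 7.2.5.2 opens: "To assess the single dose PK profile of PF-04518600 PK concentrations will be listed, summarized and plotted for subjects in the PK analysis set", with a pointer to Section 5.4. The list of presentations that follows is introduced for PF-04518600, and there is no matching list for utomilumab. Protocol 9.5.1 says: "The concentrations of PF-04518600 (Parts A and B) and utomilumab (Part B only) will be summarized descriptively by dose, cycle, and nominal time", and adds individual and median profiles by dose and cycle.

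**Precedence.** SAP Section 2: "This SAP supersedes the statistical considerations identified in the protocol". The same paragraph says that the SAP supplements the protocol and that substantial differences will be identified.

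**The concern.** An analysis-set definition is an instruction to the programmer. This one sets a condition that three of the four study parts cannot meet. A programmer who follows it drops the escalation cohorts and the combination expansion from the concentration tables. One who does not follow it departs from the SAP, and SAP Section 2 requires such departures to be described in the study report. The literal reading would also leave the parameter tables resting on patients whose concentrations appear in no concentration table.

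The utomilumab gap is a separate matter. PK of both drugs in combination is a secondary objective in Parts B1 and B2, and SAP 5.10 confirms that utomilumab samples are collected, yet SAP 7.2.5.2 plans no listing, summary or plot of them.

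Concentration data carry weight in this trial. Protocol 3.1.1.2 chose the 30 mg dose partly by reference to trough concentrations. Protocol 1.2.1.6 reports lower troughs in three Part A1 patients with high anti-drug antibody titres. The PK sampling schedules fall to pre-dose samples only from Cycle 7. Such samples add little to AUC-type parameters, so concentration summaries are their main descriptive home.

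**Working it through.** The plan gives no figure to reproduce here. The check compares the set definition with the allocation in each part, counts the patients affected, and compares the planned outputs drug by drug.

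**Step 1. Planned numbers and allocation.** SAP counts come from SAP 2.1 (A1, A2, B1) and SAP 3 (B2, 20 per arm at full enrolment). Protocol counts come from 3.1.1.1, 3.1.1.2, 3.1.2.1 and 3.1.2.2. All are approximate or upper figures.

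| Part | SAP | Protocol | Randomised |
|---|---|---|---|
| A1 | 58 | 58 | No: sequential dose cohorts |
| A2 | 2 × 20 = 40 | 2 × 20 = 40 | Yes, 1:1 |
| B1 | 53 | 55 | No: sequential dose-combination cohorts |
| B2 | 2 × 20 = 40 | 2 × 20 = 40 | No: arms are tumour types |
| Total | 191 | 193 | |

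**Step 2. Patients outside the literal set** (total minus A2):
- SAP counts: 58 + 53 + 40 = 151; 151/191 = 79%.
- Protocol counts: 58 + 55 + 40 = 153; 153/193 = 79%.

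**Step 3. Sensitivity to the optional 800 mg level in A2** (protocol 3.1.1.2). Its size is not given. Assuming 20 further randomised patients:
- SAP counts: 151/(191 + 20) = 151/211 = 72%.
- Protocol counts: 153/(193 + 20) = 153/213 = 72%.

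The totals of 211 and 213 are close to the stated maximum of approximately 210, but neither document gives that breakdown.

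**Step 4. Utomilumab.** Patients due to receive it are B1 + B2: 53 + 40 = 93 on SAP counts, 55 + 40 = 95 on protocol counts. SAP 7.2.5.2 plans utomilumab concentration output for none of them; protocol 9.5.1 requires it in Part B. This result does not depend on how the word randomized is read.

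**Step 5. What is unaffected.**
- *Parameters.* SAP 5.10 defines PK parameters for PF-04518600 in all parts and for utomilumab in B1 and B2. SAP 7.2.5.1 plans one parameter table across all cohorts and a dose-relationship plot per analyte.
- *Later PF-04518600 cycles.* The lead-in to 7.2.5.2 speaks of a single dose, but its listing and summary run by cycle, so later cycles are included.

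**The case against.** The strongest reply is that randomized is a loose, study-wide word in this SAP. Section 5.8 starts PFS at randomisation and lists the randomisation date among the dates of last contact; 5.6.1 and 5.6.2 divide protocol deviations into those before and after randomisation. Read strictly, PFS would have no start date in A1, B1 and B2. SAP 7.2.5.2 also overlays all doses in one figure, which fits poorly with a set limited to two flat doses. Finally, 7.2.5.2 does not name the 5.4.1 set: it points to a PK analysis set in Section 5.4, which holds two, and 7.2.5.1 uses the same phrase for parameters.

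Much of this stands. It makes inadvertence the likely explanation, and it means that the use of the 5.4.1 set for concentrations is the natural reading of the pointer, not an explicit instruction. It does not make the definition right, and the ambiguous pointer is a further reason to edit.

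Three stronger readings are tempting but unsupported:

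- *That PK data for most patients, or utomilumab PK as a whole, are lost.* The secondary PK endpoints are parameters, and the parameter set and outputs keep all cohorts and both drugs.
- *That multiple-dose PF-04518600 concentrations are dropped.* The by-cycle outputs include them.
- *That the SAP deliberately cancels protocol 9.5.1.* SAP Section 2 also describes the SAP as a supplement and promises to identify substantial differences. None is identified on this point in the readable text, so silence may equally mean oversight. The documents leave open whether 9.5.1 still applies, and an analysis plan should settle that.

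The section after 7.2.5 is redacted and cannot be checked. However, 7.2.5.2 is the section headed for PK concentrations, and it is legible.

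**Conclusion.** The point holds as two defects confined to concentration output. First, the definition in SAP 5.4.1 is wrong as written: taken literally, it excludes Parts A1, B1 and B2, about 79% of planned patients, or about 72% under the assumed 20-patient optional arm. Those shares rest on approximate planned numbers and on 5.4.1 being the set that 7.2.5.2 intends. They measure what the wording excludes and are not a forecast of what the sponsor would do. Second, SAP 7.2.5.2 omits utomilumab concentrations for about 93 to 95 Part B patients, against protocol 9.5.1 and without flagging the difference.

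No dose-escalation rule or PK parameter endpoint changes. The correction should nevertheless be made before database lock, because the set rule cannot sensibly be applied as it stands and one drug's concentration output is unspecified.

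**What to change.** - **SAP 5.4.1:** replace randomized with enrolled, so that the set holds enrolled and treated patients with at least one measurable concentration. It could then hold up to about 191 (SAP) or 193 (protocol) planned patients, not about 40.
- **SAP 7.2.5.2:** name the 5.4.1 set in place of the general pointer to Section 5.4. Remove the single-dose limit from the lead-in, so that it agrees with the by-cycle outputs beneath it. Apply the same listings, summaries and plots to utomilumab in Part B, matching protocol 9.5.1.

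The cost is a few wording edits in two SAP sections and rerunning the same table, listing and figure programs for a second analyte. The utomilumab samples are already scheduled, so no new data collection is needed.
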